9.3.4 Sensitivity analyses

We will conduct sensitivity analyses as follows:

1. Discontinuation will be defined as no subsequent prescriptions within 4 months of last prescription date.
2. Treatment patterns of medication use for MHT by index treatment classes with patients for 2 years of follow-up.

9.4. Data sources

Health Insurance Review and Assessment service (HIRA) database

This study will use the claims data of HIRA from January 1, 2011 to December 31, 2020. The National Health Insurance in South Korea covers approximately 98% of the entire Korean population. Under the terms of universal health coverage, all the claims data for reimbursement filed by healthcare providers are collected in HIRA database. This database contains a comprehensive information for healthcare services provided to beneficiaries such as diagnoses, treatment, procedures, surgical history, and prescription drugs. It includes an anonymized identifier, which represents the individuals in claims data, with age, sex, inpatient and outpatient diagnoses and drug prescriptions. The diagnoses are coded in compliance with KCD-8 which is a modified codes based on the International Classification of Disease, 10th revision (ICD-10). Information on prescribed drugs included generic name, prescription date, duration, and type of administration. Previous validation studies have been conducted to compare the diagnoses entered in the claims database with the actual diagnoses recorded in the patients' medical records from hospital or clinic chart review. The overall positive predictive value of the diagnoses in the South Korean healthcare database is 82%.

Korean Statistical Information Service (KOSIS)

The KOSIS was established by the Korean National Statistic Office in July 2007 under the national information strategy scheme. It is a statistical information system open to public that provides a

convenient access to wide variety of statistics. It currently provides more than 343 types of statistics produced by 120 organizations in South Korea. Moreover, KOSIS releases 100 major indicators of Korea, which provides information on health indicators and social status including mid-year population of each year and census population for each year.

9.5. Study size

The objectives of the analysis are descriptive in nature. Therefore, the sample size calculations are not applicable. Instead, we estimated the expected number of patients with MHT using a medical claims volume search tool operated by HIRA (available at:

<http://opendata.hira.or.kr/op/opc/olap3thDsInfo.do>

This search tool provides the number of diagnosis codes filed for reimbursement to HIRA classified by age and sex of beneficiaries. We retrieved the number of patients between age of 40-59 with menopausal and other perimenopausal disorders (KCD-8 code: N95) recorded as primary diagnosis codes from 2012 to 2019 via this public search tool (Table 7). The number of patients with menopausal and other perimenopausal disorders was similar over the recent 4 years, and we identified 4,293,747 female patients with menopausal and other perimenopausal disorders in total as of 2012 to 2019.

We plan to include patients who were diagnosed with menopausal symptoms between January 1, 2012 and December 31, 2019 as our study cohort study which is likely to have sufficient power for the study.

Table 7. Number of diagnosis code (KCD-8: N95) filed for reimbursement to HIRA from 2012 to 2019

age	2012	2013	2014	2015	2016	2017	2018	2019
40 - 44	23,651	22,014	19,679	17,840	16,928	15,733	14,432	13,477
45 - 49	117,078	109,784	101,951	95,700	93,679	91,211	86,927	84,398
50 - 54	264,843	257,496	235,877	223,231	211,798	204,688	198,718	203,940
55 - 59	186,203	185,308	185,719	190,210	199,122	206,497	207,747	207,868
Total	591,775	574,602	543,226	526,981	521,527	518,129	507,824	509,683

9.6. Data management

A Principal Investigator will obtain a customized HIRA database between January 1, 2011 and December 31, 2020. It is secondary data in which events or outcomes already had occurred at the time of data collection. As the information of subjects in the database is all de-identified, this study is free of any personal information issues. Access to the database is only permitted to individuals who submit the registration form to HIRA. All data management will be conducted on secure servers with regular backups. We will perform all statistical analyses using SAS version 9.4 (SAS Institute Inc., Cary, NC, USA). This study was approved by the Sungkyunkwan University's Institutional Review Board (SKKU-IRB- 2022-11-005).

9.7. Data analysis

We will investigate the baseline characteristics of patients with MHT. Baseline characteristics such as age, insurance type and income levels, and medical institution type will be assessed on cohort entry date. Baseline characteristics such as CCI, no. of outpatient visits/hospitalization, comorbidities and concomitant medications will be assessed on during a 1-year period before cohort entry date. Type of administration will be assessed on index date. The results will be presented in frequency (proportion) for categorical variables and mean (SD) or median (IQR) for continuous variables.

All outcome variables will be summarized descriptively through the tabular or graphical form of means, medians, ranges, and standard deviations of continuous variables and frequency distributions of categorical variables.

Annual time-series prevalence of menopausal symptoms and use of MHT will separately be calculated among total women aged 40-59.

The prevalence of each menopausal symptom among patients with MHT will be calculated as the number of patients diagnosed with each menopausal symptom divided by the number of patients diagnosed and prescribed for MHT. Menopausal symptoms, assessed within 90 days after the cohort entry date, will be classified into 4 categories: vasomotor symptoms, bone and joint symptoms, genitourinary symptoms, and psychosomatic symptoms.

We will examine annual and quarter time-series trends in the prevalence of use for MHT by treatment class, age group, menopausal symptoms, and the type of administration between 2012 and 2020.

We will examine annual and quarterly time-series trends in the prevalence of MHT use by 3 types of MHT: ET (estrogen therapy), EPT (estrogen-progestin therapy), and tibolone. The time-series trend will be presented as the proportion of each type of MHT quarterly, calculated as the number of patients receiving each type of MHT divided by the total number of patients prescribed with MHT.

We will examine annual time-series trends in the prevalence of MHT use by age group: all ages, 40-44, 45-49, 50-54, and 55-59. The time-series trend will be presented as the proportion of MHT use by each age group, calculated as the number of patients in each age group divided by the total number of patients prescribed with MHT.

We will examine annual time-series trends in the prevalence of use for MHT by menopausal symptoms: vasomotor symptoms, bone and joint symptoms, genitourinary symptoms, and psychosomatic symptoms. The time-series trend will be presented as the proportion of MHT use by each menopausal symptom, calculated as the number of patients with each menopausal symptom divided by the total number of patients prescribed with MHT.

We will examine annual time-series trends in the prevalence of use for MHT by the type of administration: systemic HT (oral), systemic HT (transdermal) and local HT (transvaginal). The time-series trend will be presented as the proportion of MHT use by each type of administration, calculated as the number of patients with MHT by each type of administration divided by the total number of patients prescribed with MHT.

Switching and discontinuation of MHT for any other MTH type will be shown by using Kaplan-Meier curve. Discontinuation will be defined as no subsequent prescriptions within 2 months of last prescription date. We will conduct a sensitivity analysis where discontinuation of MHT is defined as a 4-month period without any MHT.

Treatment persistence is calculated by the average length of treatment of the drugs that were prescribed at the index date. Treatment adherence will be shown by calculating MPR (medication possession ratio), calculated as a total number of days of supply of medication divided by the number of days of the follow-up period.

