 - Prevalence of each menopausal symptom including vasomotor symptoms, bone and joint symptoms, genitourinary symptoms, and psychosomatic symptoms will be calculated among patients with MHT.

- Within final study cohort, prevalence of menopausal hormone therapy by treatment class, age group, menopausal symptoms and the type of administration will be calculated for each year.
- Baseline characteristics including demographic characteristics, medical institution type, proxies of health status, comorbidities, and concomitant medications will be assessed on cohort entry date or within 365 days prior to cohort entry date. Type of administration will be assessed on index date. The baseline characteristics of patients with menopausal symptoms will be presented in frequency (proportion) for categorical variables and mean (standard deviation, SD) or median (interquartile ranges, IQR) for continuous variables.
- All outcome variables will be summarized descriptively through tables or graphical forms, including means, medians, ranges, and standard deviations of continuous variables, as well as frequency distributions of categorical variables.
- We will evaluate annual and quarterly time-series trends in the prevalence of MHT between 2012 and 2020 from 4 dimensions: 1) treatment class of MHT: ET (estrogen therapy), EPT (estrogen-progestin therapy), and tibolone. 2) age group: all, 40-44, 45-49, 50-54, and 55-59. 3) menopausal symptoms: vasomotor symptoms, bone and joint symptoms, genitourinary symptoms, and psychosomatic symptoms. 4) type of administration: systemic HT (oral), systemic HT (transdermal), and local HT (transvaginal).
- For treatment change pattern analysis, the treatment will be categorized and the proportional flows of patients switching the treatment classes will be demonstrated by Sankey diagram.
- Kaplan-Meier survival curves will be generated to calculate the time to non-persistence events including switch and discontinuation. Discontinuation will be defined as no subsequent prescriptions within 2 months of last prescription date.
- Treatment persistence is calculated by the average length of treatment of the drugs prescribed at the index date. Persistence rate at 3-, 6-, 9-, and 12-month were also calculated.
- Treatment adherence will be evaluated using medication possession ratio (MPR) calculated as the total number of days of medication supply divided by the number of days in the follow-up period.

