9.3.2 Outcomes

We will examine the treatment patterns of patients with MHT.

- 1) Prevalence of menopausal symptoms and use of MHT among women aged 40 – 59 years.
 - The annual prevalence of menopausal symptoms will be calculated as the number of women diagnosed with menopausal symptoms divided by the mid-year population of women aged 40 – 59 years.
 - The annual prevalence of menopausal symptoms with MHT will be calculated as the number of women diagnosed with menopausal symptoms and prescribed with MHT divided by the mid-year population of women aged 40 – 59 years.
- 2) Prevalence of each menopausal symptom among patients with MHT.
 - Menopausal symptoms will be classified into 4 categories: vasomotor symptoms, bone and joint symptoms, genitourinary symptoms, and psychosomatic symptoms. (Table 3)
 - The prevalence of each menopausal symptom among patients with MHT will be calculated as the number of patients diagnosed with each menopausal symptom divided by the number of patients prescribed for MHT.

Table 3. Menopausal symptoms

Menopausal symptoms	KCD-8 code
Vasomotor symptoms	N95.1 (Menopausal and female climacteric states) N95.3 (States associated with artificial menopause) N95.8 (Other specified menopausal and perimenopausal disorders) N95.9 (Menopausal and perimenopausal disorder, unspecified) R23.2 (Flushing) [§]
Bone and joint symptoms	M80.0 (Osteoporosis with pathological fracture) M81.0 (Postmenopausal osteoporosis) M81.99 (Osteoporosis, unspecified, site unspecified; Osteopenia)

	M85.99 (Disorder of bone density and structure, unspecified, site unspecified; Osteopenia, mild; Osteopenia, moderate; Osteopenia, severe)
Genitourinary symptoms	N94.1 (Dyspareunia) N95.0 (Postmenopausal bleeding) N95.2 (Postmenopausal atrophic vaginitis) F52.6 (Nonorganic dyspareunia)§
Psychosomatic symptoms	F32 (Depressive episode)§ F33 (Recurrent depressive disorder)§ F51 (Nonorganic sleep disorders)§ G47 (Sleep disorders)§

§R23.2, F32, F33, F51, F52.6, G47 are considered as diagnosis codes for menopausal symptoms only when they are obtained by obstetrics and gynecology specialists. (DGSBJT_CD:10)

- 3) Secular trend in the prevalence of MHT by treatment class, age group, menopausal symptoms, and the type of administration
 - We will examine annual and quarterly time-series trends in the prevalence of MHT between January 1, 2012, and December 31, 2020.

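### Outcome 1 is one crude annual prevalence for all women aged 40-59, so a shift in the band's age structure can move the series with no change in any age-specific rate, by an amount and in a direction the documents do not determine

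*Combined protocol and SAP*

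**What the plan says.** Section 9.3.2, item 1, defines two population prevalences, each over the whole 40-59 band. The first is given as follows: "The annual prevalence of menopausal symptoms will be calculated as the number of women diagnosed with menopausal symptoms divided by the mid-year population". The second counts women with both a symptom diagnosis and an MHT prescription, and is likewise "divided by the mid-year population of women aged 40 – 59 years". Section 9.7 makes these a yearly series: "Annual time-series prevalence of menopausal symptoms and use of MHT will separately be calculated among total women aged 40-59". The denominators come from KOSIS, which section 9.4 describes as "including mid-year population of each year and census population for each year".

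Age enters the trend analyses in only one other way. The age-group trend in sections 9.3.2 (item 3) and 9.7 is "calculated as the number of patients in each age group divided by the total number of patients prescribed with MHT". The abstract (section 4) also mentions prevalence by age group, but places it inside the cohort: "Within final study cohort, prevalence of menopausal hormone therapy by treatment class, age group, menopausal symptoms and the type of administration will be calculated". The sensitivity analyses in section 9.3.4 vary the discontinuation gap and the length of follow-up, and nothing else. No section plans age standardisation or a population prevalence by age band.

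**The concern.** A prevalence over a 20-year age band is a weighted average of the prevalences within it, with the population's age distribution as weights. If prevalence differs by age and the weights move from year to year, the average moves too, even when nothing changes for women of any given age. Table 7 in section 9.5 gives reason to take this seriously: patient counts differ sharply across the four bands, and their mix changes steadily over the study years.

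The age-group trend does not help. Its denominator is all MHT users, so the four shares always add to 100% and cannot show whether use at a given age rose or fell. Symptom prevalence has no age breakdown at all. Outcome 1 is the only series with a population denominator, so it is where a reader will look to learn whether diagnosis or treatment became more or less common among Korean women. The risk is that a change in age structure is reported as a change in diagnosis or use, or conceals one.

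**Working it through.** **Inputs.** All counts come from the table titled "Table 7. Number of diagnosis code (KCD-8: N95) filed for reimbursement to HIRA from 2012 to 2019" in section 9.5. Its first row reads "40 - 44 23,651 22,014 19,679 17,840 16,928 15,733 14,432 13,477".

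| Age | 2012 | 2019 | Change | Share 2012 | Share 2019 |
|---|---|---|---|---|---|
| 40-44 | 23,651 | 13,477 | -43.0% | 4.0% | 2.6% |
| 45-49 | 117,078 | 84,398 | -27.9% | 19.8% | 16.6% |
| 50-54 | 264,843 | 203,940 | -23.0% | 44.8% | 40.0% |
| 55-59 | 186,203 | 207,868 | +11.6% | 31.5% | 40.8% |
| Total | 591,775 | 509,683 | -13.9% | | |

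**Step 1: reproduce the plan's figures.** All eight annual totals in Table 7 equal the sum of their four age rows, and together they give the stated 4,293,747.

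**Step 2: are both conditions for a composition effect visible?** Counts in 2012 differ 264,843 / 23,651 = 11.2-fold between 50-54 and 40-44. The 55-59 share of patients rises by 40.8 - 31.5 = 9.3 points. These are counts. Reading them as rates needs the population by age, which the documents do not give.

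**Step 3: illustrate the effect.** Assumptions, none of them from the documents: each band holds 25% of women aged 40-59 in 2012; age-specific rates stay at their 2012 level; a fraction s of the population moves from one band to another. With counts c, the relative change in crude prevalence is

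s × (c_to - c_from) / (591,775 / 4) = s × (c_to - c_from) / 147,944.

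| Shift | c_to - c_from | s = 2 points | 4 points | 6 points |
|---|---|---|---|---|
| 40-44 to 55-59 | +162,552 | +2.2% | +4.4% | +6.6% |
| 40-44 to 50-54 | +241,192 | +3.3% | +6.5% | +9.8% |
| 50-54 to 55-59 | -78,640 | -1.1% | -2.1% | -3.2% |

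A directly standardised prevalence would show 0% in every cell.

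**Step 4: what fixes the sign?** The third row is negative because, with equal bands, the implied rate at 55-59 is below that at 50-54. It stays negative as long as the 55-59 population is more than 186,203 / 264,843 = 70.3% of the 50-54 population. So the sign depends on which bands gain and lose, and on population figures that are not in the documents.

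**Step 5: vary the equal-bands assumption.** Three other assumed 2012 distributions (27/26/26/21%, 28/25/25/22% and 22/26/26/26%) were run alongside equal quarters. The shifts were 1, 3 or 5 points towards older groups: from the younger half to the older half, from 40-44 to 55-59, or from the three younger bands to 55-59. Crude prevalence changed by +0.3% to +6.8%. None of these runs took the whole shift from 50-54, which is the case that gives a fall in Step 3.

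**The case against.** The strongest reply is that the study is descriptive and crude prevalence is the right measure of how many women are diagnosed or treated. Section 9.3.2 defines Outcome 1 as an annual prevalence and lists secular trend as a separate outcome, and no section says the Outcome 1 series will be read as change independent of age. This stands in part. The crude figure is valid as burden and should stay. But section 9.7 presents it as a time series, and the separate trend outcome has formulas that are shares of MHT users, so it cannot answer the population question.

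A second reply concerns the evidence, and it stands in full. Table 7 covers N95 as primary diagnosis. Eligibility also uses the osteoporosis and osteopenia codes in Table 1 and allows secondary diagnoses, and Table 7 holds no MHT prescriptions. It is therefore partial evidence for the symptom series and only indirect evidence for the MHT series.

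A reader might draw three stronger conclusions, none of which the documents support:

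- **That ageing within the band must push crude prevalence up.** The shift from 50-54 to 55-59 lowers it under the same assumptions.
- **That the effect can be sized against the 13.9% fall in N95 counts.** That is a change in raw counts, while the planned series divides by a population that also moves, so the two are not comparable.
- **That Table 7 demonstrates population ageing.** Falling counts at ages 40-54 could come from fewer women, lower diagnosis rates, or both.

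**Conclusion.** The gap is real: the only series with a population denominator is crude over a 20-year band, and nothing else in the plan lets a reader separate age structure from change at a given age. What follows is a possible distortion when the series is read as a trend, not a demonstrated bias. Its sign and size cannot be known without the KOSIS population by age for each year. For a population shift of 2 to 6 points between two bands, the illustrations run from -3.2% to +9.8% (relative). They rest on equal population bands, rates proportional to 2012 N95 counts and held constant, and assumed shifts. They show that the effect need not be negligible and can go either way; they do not estimate it. The result for MHT use rests on the general argument, because the documents give no MHT counts by age.

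**What to change.** Keep the crude annual series and label it as the measure of burden. In section 9.3.2 (item 1) and section 9.7, add the following for symptoms and for symptoms with MHT:

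1. Annual prevalence in 40-44, 45-49, 50-54 and 55-59, with the HIRA numerator over the KOSIS mid-year female population of the same band.
2. A directly age-standardised 40-59 series: the sum over bands of fixed weight × band prevalence, with weights from the KOSIS age distribution of one reference year named in advance (2016, for example).
3. A statement that any conclusion about change over time in diagnosis or use, as distinct from burden, refers to the age-specific or standardised series.

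The cost is a small amount of extra analysis and one extra line per figure. HIRA already records age and sex, and the plan already needs the KOSIS population of women aged 40-59 by year. The only additional input is that population split into the protocol's own four age groups, which is assumed here to be obtainable.

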9.8. Quality control

The HIRA data is first generated in the process of reimbursement under the National Health Insurance Service, a government agency, in South Korea. Claims for which reimbursement decision

has been completed are collected in the database, managed regularly by the HIRA, and then processed to be provided for research purposes. Thus, the general requirements for quality control in clinical trials are unnecessary for this study. All data will be checked for completeness and outlying values by a research group with requisite background and experiences in pharmacoepidemiology. The statistical analysis will be independently conducted by two researchers who are skilled in using the SAS program and cross-checked to guarantee the accuracy of the analysis. We will archive all data files, data management, and statistical programs for quality control.

9.9. Strengths and limitations of the research methods

Due largely to its nature of medical claims data, there are some inbuilt limitations. Firstly, discrepancies occur between diagnoses entered in HIRA data and diseases that a patient actually has in reality. Such discrepancies may arise from the inherent nature of claims data, in which the diagnostic codes used for reimbursement might reflect suspected clinical diagnoses rather than confirmed clinical diagnoses. In addition, there is a lack of clinical laboratory data and other clinical markers. Lastly, claims data only provide information on filled prescriptions, not medications actually used. It is also applicable for non-reimbursable diagnosis, treatment or medications. These limitations are generally undetectable or unsolvable, but the dominant majority of data is valid according to the previous studies on the feasibility of the NHIS (National Health Insurance Service) and the HIRA claims data in South Korea. Despite these limitations, we will use HIRA data because it has enormous valuable information representing the entire population of South Korea. We expect to produce real-world evidence on current trends in MHT in South Korea.

